### **8.5.5 AMG 334 Antibody testing**

Blood samples for antibody testing are to be collected for the measurement of anti-AMG 334 binding antibodies. Samples will be collected at the timepoints defined in [Table 8-1](#), prior to study drug administration. Samples testing positive for binding antibodies will also be tested for neutralizing antibodies and may be further characterized for quantity/titer, isotype, affinity, and presence of immune complexes. Additional blood samples may be obtained for further evaluation of anti-AMG 334 antibodies during the study.

Sites will not be notified of positive neutralizing antibody results to the investigational product for a subject prior to that subject's final scheduled study visit and the subjects with a positive neutralizing antibody response will continue to be dosed during the course of study.

During the **COVID-19 pandemic** that limits or prevents on-site study visits, or if visits by site staff to a subject's home are not feasible, the collection of samples may be modified by Novartis and will be communicated to the investigator.

## **9 Study discontinuation and completion**

### **9.1 Discontinuation**

#### **9.1.1 Discontinuation of study treatment**

Discontinuation of study treatment for a subject occurs when study drug is stopped earlier than the protocol planned duration, and can be initiated by either the subject or the investigator.

The investigator must discontinue study treatment for a given subject if, on balance, he/she believes that continuation would negatively impact the risk/benefit of trial participation.

Study treatment must be discontinued under the following circumstances:

- Subject/Guardian decision
- Pregnancy (See [Section 8.4.3](#))
- Use of prohibited treatment as per recommendations in [Section 6.2.2](#)
- Any situation in which study participation might result in a safety risk to the subject
- Any laboratory abnormalities that in the judgment of the investigator, taking into consideration the subject's overall status, prevents the subject from continuing participation in the study
- Following emergency unblinding (during the double-blind treatment period)

In addition, study treatment should be discontinued under the following circumstances during the open-label treatment period:

- Upon launch of erenumab in the country or in June 2021 in Korea
- Subject is no longer clinically benefitting in the opinion of the investigator

If discontinuation of study treatment occurs during the double-blind or open-label treatment period, the subject should NOT be considered withdrawn from the study (unless the subject specifically withdrew the consent). The Subject should return to the clinic at the time of the next scheduled visit (4-weeks interval), for the 'End of Treatment' or 'End of Treatment Open-Label' visit respectively. Assessments detailed for this visit in [Table 8-1](#) should be completed

and recorded in the appropriate CRF. The investigator should make a reasonable effort to understand the primary reason for the subject's premature discontinuation of study treatment and record this information on the appropriate CRF.

Subjects who discontinue the study treatment in the double-blind treatment period and are willing to return for the subsequent scheduled Follow-Up (FUP) visits should perform the End of Treatment assessments at the time of the next scheduled visit (4-weeks interval). The subject will then continue the subsequent FUP visits as per [Table 8-1](#), including the Safety Follow-Up visit on Week 20.

All subjects ongoing in the treatment period at the time of a positive IA read-out will be scheduled for an End of Treatment visit and then enter directly into the open-label treatment period or into the safety Follow-Up Period (in case the subject does not want to continue in the open-label treatment period) without performing those FUP visits.

Subjects who discontinue the study treatment in the double-blind treatment period and are NOT willing to return for the subsequent FUP visits should perform the assessments according to the End of Treatment visit as soon as possible and the following data should be collected after study treatment discontinuation and until the Safety Follow-Up visit (which should occur 12 weeks after the last dose):

- new / concomitant treatments
- adverse events/Serious Adverse Events

If the subject who discontinued study treatment in the double-blind treatment period cannot or is unwilling to attend the End of Treatment visit or the Safety Follow-Up visit, the site staff should maintain telephone contact with the subject, or with a person pre-designated by the subject.

Subjects who discontinue the treatment during the open-label treatment period and performed the End Of Treatment visit will not be allowed to re-enter the study.

The investigator must also contact the IRT to register the subject's discontinuation from study treatment.

If study drug discontinuation occurs because the treatment code has been broken, please refer to [Section 6.6.2](#). Subjects who are prematurely withdrawn from the study will not be replaced by an equal number of newly enrolled subjects.

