 Entry (i.e. randomization) into the double-blind treatment period using the IRT System must occur only after the successful completion of all Screening Period requirements and prior to the first dose of study drug (randomization and administration of the first dose must occur on Day 1).

 Week 4 FUP, Week 8 FUP, Week 12 FUP are to be performed by discontinued subjects (double-blind treatment period) who are willing to remain on the study to perform regular assessments.

 The Safety Follow-Up Visit is required for all subjects who either discontinue study drug in the double-blind treatment period or complete the double-blind treatment period without continuing in the open-label treatment period. Safety Follow-Up Visit is 12 weeks after last dose of study treatment during the double-blind treatment period. For patients discontinuing treatment during the double-blind treatment period and remaining on the study to follow the assessment schedule until Week 12 Follow-Up (FUP) visit, Safety Follow-Up visit should occur on Week 20 even if last dose was taken at Day 1.

 Sites will access the Interactive Response Technology (IRT) System to enter the subject into the initial screening period, to randomize an eligible subject into the

double-blind treatment period, to dispense study treatment during the double-blind and open-label treatment periods, and to register study early termination. Subject data will be collected in the IRT System including, but not limited to, reason for screen fail (if applicable). The IRT system will automatically assign study drug when a subject is randomized.

 Including prior prophylactic migraine medication

 Height collected at Screening visit only. Weight collected at Screening, Baseline, and End Of Treatment (double-blind treatment period) visits. Blood pressure, pulse and body temperature collected at every double-blind treatment period visit.

 At Day 1 visit sample should be collected prior to dose administration.

 Subject brings the eDiary device to each double-blind treatment visit for use at site.

 Subjects will record headache and headache medication information daily, using the provided eDiary device, during the double-blind treatment period.

 Completed daily via the eDiary device, during the double-blind treatment period.

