## 8.3 Efficacy

Efficacy assessments will include:

- Migraine days

The timing and frequency of these assessments are outlined in [Table 8-1](#). Subjects will record the efficacy information using the provided eDiary platform. To aid in compliance, it is recommended that the information be completed at the same time every day that is convenient for the subject. Retroactive completion will be allowed one day prior to the time of completion. Any entries > 2 days old will not be allowed and will be considered missing data.

During the COVID-19 pandemic that limits or prevents on-site study visits, efficacy information including PRO scales may still be collected by using the provided eDiary.

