### **8.5.2 Patient Reported Outcomes (PROs)**

The eDiary will collect the following patient-reported outcomes (PRO) until the end of the double-blind treatment period:

- mMIDAS, monthly
- [REDACTED]
- [REDACTED]
- Beck Depression Inventory, screen

For those PROs that are completed during the site visit, subjects must complete the PROs before any clinical assessments are performed.

Subject questionnaires as well as the COAs should be completed in the language most familiar to the subject. The subject should be given sufficient space and time to complete the PRO measure(s).

The responses (COAs and PROs) stored electronically in the database will be considered the source file.

Site staff will review eDiary compliance with the patient at each applicable visit.

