Monthly efficacy measurements will be calculated based on the subject's monthly investigational product (IP) dosing schedule defined below using eDiary data collected from beginning of the baseline period (Week -4 visit) up to the End of Treatment in DB period (Week 12 visit).

Table 2-3 Study Intervals for Efficacy Endpoints

Study Phase	Assessment Time point	Interval Based on Dose Dates	
		Start date	End date
Baseline Period	Baseline	From eDiary device assignment date (or Week -4 visit)	Day prior to study day 1
DB Period	Week 4	Study Day 1	
• Week 4 dose date-1• Study day 28 if Week 4 dose is not received (either missed or IP discontinued prior to Week 4) 
Note: if day 1 dose is the last IP dose subject received, the rest of monthly assessments during treatment period will be calculated based on consecutive 28-day interval beginning on study day 29 (ie, 29-56 for week 8, 57-84 for week 12)

	Week 8	
• Week 4 dose dateStudy day 29 if Week 4 dose is not received (either missed or IP discontinued prior to Week 4)	
• Week 8 dose date-1Study day 56 if Week 8 dose is not received (either missed or IP discontinued prior to Week 8)
	Week 12	
• Week 8 dose dateStudy day 57 if Week 8 dose is not received (either missed or IP discontinued prior to Week 8)	
MIN (Study day 84, EoS) if Week 8 dose is not received
 
MIN (Week 8 dose date + 28, EoS) if week 8 dose is received

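### Protocol 9.1.1 omits the home eDiary for discontinuers who decline follow-up visits, so their Week 9-12 primary value is usually missing although they are still being followed

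*Protocol*

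**What the plan says.** Protocol 9.1.1 does not count a subject who stops study treatment as withdrawn unless consent is withdrawn. It then separates two groups.

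- **Willing to return:** End of Treatment assessments at the next scheduled visit, then the follow-up visits of Table 8-1.
- **Not willing to return:** End of Treatment assessments as soon as possible. After that, "the following data should be collected after study treatment discontinuation and until the Safety Follow-Up visit" ("which should occur 12 weeks after the last dose"). The list has two items: "new / concomitant treatments" and "adverse events/Serious Adverse Events". Telephone contact is kept with subjects who will not attend the End of Treatment or Safety Follow-Up visit.

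The SAP provides for off-drug values. In Table 2-3 (section 2.1.3) the Week 12 interval starts on Study Day 57 for a subject without the Week 8 dose and ends at "MIN (Study day 84, EoS) if Week 8 dose is not received". SAP 5.1.5.1 sets a month with fewer than 14 diary days to missing. The primary model uses observed monthly data without imputation (SAP 2.5.2 and 2.5.3), and the 50% responder analysis counts missing as non-response (SAP 2.6.3).

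Protocol 8.5.1 describes the eDiary as a daily home instrument. For periods when COVID-19 limits site visits, Protocol 8.3 states that "efficacy information including PRO scales may still be collected by using the provided eDiary".

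**The concern.** The efficacy analysis covers all randomised subjects, and the SAP defines a primary value for those off drug. The protocol keeps decliners in follow-up across the whole primary window, yet asks them for no migraine data. Entering that data needs no clinic visit, and declining visits is not the same as declining a home diary.

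What is at stake is avoidable and probably informative missingness in the primary endpoint. The documents fill the gap with competing assumptions. The primary model treats the missing Week 12 value as predictable from observed data. The control-based analysis in SAP 5.1.5.3.2 takes a missing value on active drug to mean the subject is off treatment. The responder analysis scores failure. Diary entries made off drug would replace assumption with observation for any subject who keeps them.

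**Working it through.** **Inputs.** Effect 2.0 days, SD 6.8, 1:1 allocation, N = 550, 10% dropout, about 90% power, two-sided alpha 0.05, final nominal level 0.046 (Protocol 12.8.1). Retention about 95% on active treatment at 3 months in earlier trials (Protocol 4.5). Safety Follow-Up at last dose + 84 days (Protocol 9.1.1). Week 12 interval Days 57-84 without a Week 8 dose (SAP Table 2-3). Minimum 14 diary days (SAP 5.1.5.1).

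**1. The plan's own figure.** n per arm = 2 × (1.960 + 1.282)² × 6.8² / 2.0² = 243, so 486 in total, and 486 / 0.9 = 540. This agrees closely with 550. With 275 × 0.9 = 247.5 evaluable per arm, power is 90.5% at 0.05 and 89.9% at 0.046. The stated 90% reproduces.

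**2. Does follow-up cover the primary window?**

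- Last dose Day 1: 1 + 84 = Day 85.
- Last dose at Week 4 (Day 28 or 29): Day 112 or 113.

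Both fall after Day 84. SAP 2.1.1.1 defines end of study as the last date of participation. For a subject followed to that visit, the interval rule therefore returns the full Days 57-84.

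**3. Would the value be observed?** With End of Treatment as soon as possible and no diary requested afterwards, a decliner would normally have few or no diary days in Days 57-84. That is below 14, so Week 12 is missing. A subject who carried on entering data unprompted could still reach 14 days.

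**4. How many subjects?** 0.10 × 550 = 55 are all assumed dropouts. If attrition were 5% in both arms (an assumption; the cited figure is for active treatment), 0.05 × 550 = 27.5, about 28. The share who decline visits but remain contactable is not given, so the affected group is anywhere from 0 to these totals.

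**5. Upper bound on bias.** Let d be the dropout proportion and s the share of dropouts in the affected group. If all affected erenumab subjects reverted to the placebo mean and Week 4 and Week 8 data carried no information, the overstatement is at most d × s × 2.0 days.

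| d | s = 1 | s = 0.5 |
|---|---|---|
| 0.10 | 0.20 day | 0.10 day |
| 0.05 | 0.10 day | 0.05 day |

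**6. Precision and power.** SE = 6.8 × √(2/275) = 0.580 with complete data and 6.8 × √(2/247.5) = 0.611 with 10% missing. The second is what the sample size already assumes. If every dropout were retained and carried a fraction f of the effect, the overall effect is 2.0 × [(1 − d) + d × f]. Power at 0.046 is then:

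| d | none retained | f = 1 | f = 0.5 | f = 0 |
|---|---|---|---|---|
| 0.10 | 89.9% | 92.7% | 90.0% | 86.6% |
| 0.05 | 91.4% | 92.7% | 91.4% | 90.0% |

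The change is between about −3 and +3 points. The argument is about missingness, not power.

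**The case against.** The main route is already in the plan: discontinuers are offered follow-up visits, and their off-drug months are analysed. The gap concerns only those who refuse. Several objections stand and limit the point.

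- **Omission, not prohibition.** A reader might infer that the protocol excludes these data by design. It does not: nothing forbids further entries, and no text orders the device to be surrendered at End of Treatment.
- **Attenders.** A reader might infer that subjects who do attend also lose the diary, since Table 8-1 footnote 11 says "Subjects will record headache and headache medication information daily, using the provided eDiary device, during the double-blind treatment period" and Protocol 8.5.2 collects PROs "until the end of the double-blind treatment period". The documents do not support that. Table 8-1 marks eDiary return at the follow-up visits. SAP 1.1 includes post-treatment follow-up visits in completing the double-blind period, and SAP Table 2-1 runs that period to end of study for subjects not entering the open-label period. This needs clarification at most.
- **Size.** Reading 55 subjects and 0.2 day as expected values is not supported. The 55 may include consent withdrawals and losses to follow-up that no wording can reach. The repeated-measures model also uses each subject's Week 4 and Week 8 data where observed.
- **Planned sensitivity analyses.** Multiple imputation (missing at random and control-based) and BOCF already test the reversion scenario.
- **Target of estimation.** The bias bound is measured against an effect that includes off-drug outcomes. The SAP fixes the group in which each subject is analysed but states no estimand.
- **Compliance.** The COVID-19 provision shows that remote entry is feasible. It does not show that people who refuse visits will comply.

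What these objections do not answer is why a subject still being followed for adverse events and medications is not asked to continue a home diary that the SAP is ready to analyse. The sensitivity analyses vary the assumption; they do not recover the data.

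**Conclusion.** The point holds as a cheap improvement. For decliners who do not withdraw consent, follow-up under Protocol 9.1.1 covers all of Days 57-84, but the eDiary is missing from the list, so the primary value is usually missing by omission. The affected number is unknown: 0 to 55 of 550 at 10% dropout, 0 to about 28 at 5%. The bias is at most 0.2 day (0.1 day at 5%), assuming that every dropout belongs to this group, that those on erenumab revert fully to placebo, and that earlier months are not used. The realistic figure is smaller and cannot be derived from the documents. The increase in SE is not an unplanned cost, because it lies within the 10% allowance.

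**What to change.** 1. **Protocol 9.1.1.** Add to the list for subjects not willing to return: *daily eDiary (headache and acute medication), entered remotely through Study Day 84, unless the subject declines or withdraws consent*.
2. **mMIDAS.** Offer the monthly questionnaire through the eDiary on the same basis. SAP 2.1.3 and 5.1.5.1 describe office-visit collection while SAP 2.1.4.1 describes monthly eDiary completion; reconcile these.
3. **Study status.** Protocol Section 3 describes decliners as not remaining in the study for the assessment schedule, whereas 9.1.1 keeps them in follow-up. Align the two.
4. **Clarification only.** Word footnote 11 and Protocol 8.5.1-8.5.2 as *through Study Day 84, on or off study drug*. The sentence introducing SAP Table 2-3 ends diary data at End of Treatment; make clear that an early End of Treatment visit does not cut off entries before Day 84.

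**Cost.** Protocol and SAP wording, remote reminders (the telephone contact in 9.1.1 offers a channel), and later device return. A subject who stops just after Day 1 would keep the device for up to 84 − 1 = 83 days, nearly 12 weeks. Compliance is uncertain and recovery could be zero. No new instrument or visit is needed.

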### **9.1.2 Withdrawal of informed consent**

Subjects may voluntarily withdraw consent to participate in the study for any reason at any time. Withdrawal of consent occurs only when a subject:

- Does not want to participate in the study anymore  
and
- Does not allow further collection of personal data

In this situation, the investigator should make a reasonable effort (e.g. telephone, e-mail, letter) to understand the primary reason for the subject's decision to withdraw his/her consent and record this information.

Study treatment must be discontinued and no further assessments conducted, and the data that would have been collected at subsequent visits will be considered missing.

Further attempts to contact the subject are not allowed unless safety findings require communicating or follow-up.

All efforts should be made to complete the assessments prior to study withdrawal. A final evaluation at the time of the subject's study withdrawal should be made as detailed in the assessment table.

Novartis will continue to keep and use collected study information (including any data resulting from the analysis of a subject's samples until their time of withdrawal) according to applicable law.

All biological samples not yet analyzed at the time of withdrawal will no longer be used, unless permitted by applicable law. They will be stored according to applicable legal requirements.

#### **9.1.3 Lost to follow-up**

For subjects whose status is unclear because they fail to appear for study visits without stating an intention to discontinue or withdraw, the investigator must show "due diligence" by documenting in the source documents steps taken to contact the subject, e.g. dates of telephone calls, registered letters, etc. A subject should not be considered as lost to follow-up until due diligence has been completed or until the end of the study.

#### **9.1.4 Early study termination by the sponsor**

The study can be terminated by Novartis at any time for any reason.

Reasons for early termination:

- Unexpected, significant, or unacceptable safety risk to subjects enrolled in the study
- Decision based on recommendations from applicable board(s) after review of safety and efficacy data
- Discontinuation of study drug development

In taking the decision to terminate, Novartis will always consider the subject welfare and safety. Should early termination be necessary, subjects must be seen as soon as possible for End of Treatment Visit and treated as a prematurely withdrawn subject. The investigator may be informed of additional procedures to be followed in order to ensure that adequate consideration is given to the protection of the subject's interests. The investigator or sponsor depending on the local regulation will be responsible for informing IRBs/IECs of the early termination of the trial.

#### **9.2 Study completion and post-study treatment**

A subject will be considered to have completed the double-blind treatment period when the subject has completed Week 12. A subject will be considered to have completed the open-label treatment period when the subject remained in the study until erenumab is launched in the country or until June 2021 in Korea.

A subject will be considered to have completed the study when the subject has completed the last visit as per the protocol. The study will be considered completed when the last subject completes their last visit planned in the protocol.

Enrollment will continue at least until the time of the unblinded IA read-out. In case of positive read-out, enrollment will stop. Refer to [Section 9.1.1](#) for details on how to handle ongoing subjects. In case the study does not stop early, enrollment will continue until the full sample size.

## 10 Safety monitoring and reporting

During the **COVID-19 pandemic** that limits or prevents on-site study visits, regular phone or virtual calls will occur (at the time of every scheduled visit or more frequently if needed) for safety monitoring and discussion of the subject's health status until the subject can again visit the site.

### 10.1 Definition of adverse events and reporting requirements

#### 10.1.1 Adverse events

An adverse event (AE) is any untoward medical occurrence (e.g. any unfavorable and unintended sign [including abnormal laboratory findings], symptom or disease) in a subject or clinical investigation subject after providing written informed consent for participation in the study. Therefore, an AE may or may not be temporally or causally associated with the use of a medicinal (investigational) product.

The investigator has the responsibility for managing the safety of individual subject and identifying adverse events.

Novartis qualified medical personnel will be readily available to advise on trial-related medical questions or problems.

The occurrence of adverse events must be sought by non-directive questioning of the subject at each visit during the study. Adverse events also may be detected when they are volunteered by the subject during or between visits or through physical examination findings, laboratory test findings, or other assessments.

Adverse events must be recorded in the Adverse Events CRF under the signs, symptoms or diagnosis associated with them, accompanied by the following information (as far as possible) (if the event is serious refer to [Section 10.1.2](#)):

1. Adverse events will be assessed and graded according to the most current version of the Common Terminology Criteria for Adverse Events (CTCAEs)
2. its relationship to the study treatment. If the event is due to lack of efficacy or progression of underlying illness (i.e. progression of the study indication) the assessment of causality will usually be 'Not suspected'. The rationale for this guidance is that the symptoms of a lack of efficacy or progression of underlying illness are not caused by the trial drug, they happen in spite of its administration and/or both lack of efficacy and progression of underlying disease can only be evaluated meaningfully by an analysis of cohorts, not on a single subject

3. its duration (start and end dates) or if the event is ongoing, an outcome of not recovered/not resolved must be reported.
4. whether it constitutes a SAE (see [Section 10.1.2](#) for definition of SAE) and which seriousness criteria have been met
5. action taken regarding with study treatment.

All adverse events must be treated appropriately. Treatment may include one or more of the following:

- Dose not changed
- Drug interrupted/withdrawn
- 6. its outcome (i.e. recovery status or whether it was fatal)

Conditions that were already present at the time of informed consent should be recorded in medical history of the subject.

Adverse events (including lab abnormalities that constitute AEs) should be described using a diagnosis whenever possible, rather than individual underlying signs and symptoms.

Once an adverse event is detected, it must be followed until its resolution or until it is judged to be permanent (e.g. continuing at the end of the study), and assessment must be made at each visit (or more frequently, if necessary) of any changes in severity, the suspected relationship to the interventions required to treat it, and the outcome.

Information about adverse drug reactions for the investigational drug can be found in the Investigator's Brochure (IB).

Abnormal laboratory values or test results constitute adverse events only if they fulfill at least one of the following criteria:

- they induce clinical signs or symptoms
- they are considered clinically significant
- they require therapy

Clinically significant abnormal laboratory values or test results must be identified through a review of values outside of normal ranges/clinically notable ranges, significant changes from baseline or the previous visit, or values which are considered to be non-typical in subjects with the underlying disease. Alert ranges for laboratory and other test abnormalities are included in [Section 16.1](#)

